1.3.2.1 Infections

Serious infections due to bacterial, mycobacterial, invasive fungal, viral, or other opportunistic pathogens have been reported with orally administered JAK1 and JAK3 inhibitors. Patients with evidence of active, chronic, or latent infections or history of serious local skin infections or tuberculosis at the Screening Visit will be excluded from this study. Infections will be monitored during the study and will be reported as AEs.

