4.4 Stopping Rules

4.4.1 *Individual Patient Stopping Rules*

A patient will stop treatment with investigational agent if one or combination of the following occurs during the study:

- An infection which meets the criteria as a study medication-related SAE
- A deep venous thrombosis and/or pulmonary embolism
- Lymphoma
- Hy's law (see [Section 6.3.2.1](#))

Treatment with study medication should be temporarily interrupted in the event of severe AEs considered related to study medication, or in the event of one or more of the abnormal laboratory values in [Table 5](#).

4.4.2 *Study Stopping Rules*

The sponsor and ProPharma safety physician will meet regularly (every 4 weeks) and assess the ongoing safety of the study. Attention will be paid to the number of severe AEs and SAEs, with particular focus paid to the number of patients who meet individual patient stopping rules. PK data will be used in the assessment: events associated with high plasma levels will be considered of high significance.

If the study is stopped, a restart will not occur without agreement of the IRB and the sponsor's medical monitor.

4.5 *End of Study*

A patient is considered to have completed the study if he/she has completed all study visits.

The end of the study is defined as the date of the last visit or last procedure of the last patient in the study.

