6.1 Demographics and Other Screening Assessments

Safety assessments that are also part of the screening assessments are described in [Section 6.3](#).

6.1.1 *Medical History*

Medical history, including any ongoing illnesses, will be recorded in the eCRF, with the start date and stop date (if applicable) of the illness/condition. Medical history will be collected at the Screening Visit and updated, if necessary, on Day 1 prior to the first administration of study medication.

6.1.2 *Demographics*

Demographic data, including year of birth/age, sex, race, and ethnicity will be recorded in the eCRF.

6.1.3 *Tuberculosis Test*

An interferon gamma release assay/QuantiFERON Tuberculosis Gold Test for active/latent tuberculosis will be performed at the Screening Visit. The test will be provided by the central laboratory.

Patients who demonstrate evidence of latent tuberculosis infection (positive QuantiFERON Tuberculosis Gold Test) will only be allowed to participate in the study if there is documented evidence of a completed adequate treatment course for latent tuberculosis and if active tuberculosis is excluded per the investigator's judgment.

In case of indeterminate results, the test may be repeated once.

6.1.4 *SARS-CoV-2 Testing and Monitoring*

At Day 1, all patients entering the treatment phase of the study must have a nasopharyngeal (preferred) or oropharyngeal swab collected prior to the first dose of study medication to test for the presence of the SARS-CoV-2 virus. The sample will be sent to the study's central lab for analysis by reverse transcription polymerase chain reaction with results reported as either 'Detected' or 'Not detected' for SARS-CoV-2 viral particles. If central laboratory testing cannot be performed at the time of Day 1 (i.e., lab supplies are not yet available) and the study site is able to perform equivalent testing locally, they may choose to do so, as long as the test results are available in the patient's research chart for sponsor review. Patients should not initiate study medication

treatment in the absence of central laboratory or locally equivalent testing being performed.

Patients will be allowed to dose with study medication in the interval between sample collection at Day 1 and result reporting as long as there is no clinical suspicion of COVID-19 infection or recent significant exposure (close contact [<6 feet] for ≥ 15 minutes) of the patient to an individual with a confirmed, active infection.

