If the patient's results are positive for SARS-CoV-2 following sample collection at Day 1, the patient will be notified immediately upon receipt of the results and treatment with study medication will be permanently discontinued. The patient will be advised to begin self-isolation and self-monitoring procedures according to any applicable local, state, and/or federal health recommendations. Referral to an appropriate health care provider for management of the patient's COVID-19 diagnosis should also be made. The patient should be seen for the PTFU Visit (see [Table 1](#)) only at such time that the investigator assesses the risk for incidental transmission from viral shedding to be minimized. The patient's COVID-19 diagnosis will be reported as medical history unless the patient's clinical course progresses such that criterion for SAE reporting is met (see [Section 8.3](#)), in which case, all applicable safety reporting procedures will be followed by the site.

Sites will also have the option to perform an unscheduled test for the SARS-CoV-2 virus at any time during the treatment phase of the study should a patient's clinical presentation necessitate it in the investigator's opinion. The same notification and referral procedures, as outlined in the preceding paragraphs, should be followed by the site. However, it is expected that any COVID-19 diagnosis made from a sample collected after the initiation of study be reported as an AE per the requirements of [Section 8](#) of this protocol.

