8.3 Documenting and Reporting Adverse Events

Reporting of SAEs will begin when the patient has provided informed consent. Nonserious events that occur between receipt of informed consent and the first study medication application will be added to the patient's medical history. Reporting of nonserious AEs will begin with the first application of study medication. Nonserious events that occur between receipt of informed consent and the first study medication application will be added to the patient's medical history. Reporting of all AEs will continue through the PTFU Visit or 14 days after last administration of study medication, whichever is later.

Occurrence of AEs may be volunteered spontaneously by the patient; discovered as a result of general, nonleading verbal questioning by the study staff; or determined by physical examination or other safety assessments. All AEs will be monitored and recorded in the eCRF throughout the entire study.

For all AEs, the investigator must pursue and obtain adequate information (a description of the event, severity, time of occurrence [including whether the AE onset was before, during, or after the study medication application], duration, and any action, e.g., treatment/follow-up tests). The outcome of the event should be provided along with the investigator's assessment of the relationship to the study medication. The investigator must also assess whether the event meets the criteria for classification as an SAE.

It is the investigator's responsibility to review all documentation (e.g., hospital notes, laboratory reports, and diagnostic reports) related to an AE. Wherever possible, the investigator's diagnosis, not the individual signs and symptoms, will be documented as the AE.

Investigators are not obligated to actively seek AEs or SAEs after the patient's conclusion of study participation. However, if the investigator learns of any SAE, including death, at any time after a patient has been discharged from the study, and

he/she considers the event to be reasonably related to the study medication or study participation, the investigator must promptly notify the sponsor.

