Treatment group comparisons for categorical efficacy endpoints (IGA Response, EASI-50, EASI-75, and EASI-90) that are conducted over time will employ a logistic regression model fit at each scheduled visit separately, where appropriate. The logistic regression model will include treatment group as a factor and the baseline value and/or baseline severity of AD as a covariate. Model-based point estimates for the treatment proportions will be provided as well as model-based differences and corresponding 90% confidence intervals and 1-sided p-values.

9.4.6 *Analysis of Safety*

The FAS will be used for the analysis of safety data (AEs, clinical laboratory, vital signs, physical examination results, and ECGs).

AEs will be coded with MedDRA. TEAEs are defined as AEs with onset dates on or after the date of first administration of study medication through the end of the study, or that exist prior to the first dose and worsen with dosing. TEAEs will be presented by system organ class and preferred term in frequency tables. Patients with multiple AEs will be counted only once within each preferred term and system organ class. Key patient information for patients with an AE with an outcome of death, patients with SAEs, and patients with an AE leading to discontinuation of study medication will be listed.

Laboratory data (hematology, serum chemistry, and urinalysis) will be converted to Système International units for reporting and processing purposes. Absolute values and changes from baseline will be presented descriptively. Laboratory data outside study-specific reference ranges will be listed.

Vital signs and ECG parameters will be presented descriptively.

9.4.7 *Demographic and Baseline Characteristics*

Demographic characteristics (including age, sex, ethnicity, and race) and baseline characteristics (including height, weight, and disease characteristics) will be presented descriptively.

9.4.8 *Pharmacokinetic Endpoints*

Individual and mean plasma concentrations at each sampling time point for ATI-1777 will be listed and summarized in a tabular form including means, geometric means, ranges, standard deviations, and coefficients of variation. Mean concentrations will be plotted versus nominal time on linear and semilogarithmic scales.

9.4.9 *Handling of Missing Values*

Patients who discontinue study medication will be asked to come to each visit for the scheduled assessments up to the end of the study.

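### Protocol 6.1.4 files COVID-19 found on the pre-dose Day 1 swab as medical history unless it becomes serious, which conflicts with the protocol's own AE and TEAE rules when symptoms start or worsen after dosing

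*Protocol*

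**What the plan says.** Protocol 6.1.4 requires a swab before the first dose on Day 1 but does not make the patient wait for the result: "Patients will be allowed to dose with study medication in the interval between sample collection at Day 1 and result reporting", provided there is no clinical suspicion of COVID-19 and no recent significant exposure. If the result is positive, "treatment with study medication will be permanently discontinued", and the recording rule is "The patient's COVID-19 diagnosis will be reported as medical history unless the patient's clinical course progresses such that criterion for SAE reporting is met". For a test prompted later by the clinical picture, the same section says "it is expected that any COVID-19 diagnosis made from a sample collected after the initiation of study be reported as an AE", with no seriousness condition.

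Other sections bear on the same patient:

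- Protocol 1.3.2.1: "Infections will be monitored during the study and will be reported as AEs". Section 1.3.2.2 says the same of viral infections.
- Protocol 8.3: "Reporting of nonserious AEs will begin with the first application of study medication". Only non-serious events between consent and that first application are sent to medical history.
- Protocol 9.4.6, and the synopsis in similar terms, count as TEAEs events with onset after the first dose "or that exist prior to the first dose and worsen with dosing".
- Protocol 8.1.1 and SAP 12.6.1 define TEAEs by onset date alone, with no clause on worsening.
- Protocol 4.4.2, on the four-weekly review by the sponsor and the safety physician: "Attention will be paid to the number of severe AEs and SAEs".

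**The concern.** The sentence in 6.1.4 foresees an illness that progresses after dosing, but moves it into safety reporting only if it becomes serious. Protocol 8.2.1 separates intensity from seriousness, so an illness can be severe without being serious. Read literally, a patient who is well on Day 1, applies study drug, and becomes ill a few days later has that illness entered as medical history because of the date of the swab. If the positive swab had been taken after treatment began, the same illness would be an AE.

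Infection is the first class risk that the protocol lists for this first-in-human JAK1/3 inhibitor. What is at stake is whether a post-dose infectious illness appears in the TEAE and severe-TEAE tables and in the severe-AE count that the four-weekly review watches. With about 25 patients per arm, one patient is 1/25 = 4 percentage points of that arm's TEAE incidence.

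**Working it through.** The plan gives no figure for this point, so the main check is to apply each rule to one case. The arithmetic afterwards only shows scale.

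**The case.** The pre-dose swab on Day 1 is positive. The patient doses before the result is known. Non-serious symptoms begin, or worsen, after the first application.

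| Source | Where the illness goes |
|---|---|
| Protocol 6.1.4, Day 1 swab | Medical history, because no SAE criterion is met |
| Protocol 6.1.4, later swab (for contrast) | AE |
| Protocol 1.3.2.1 and 1.3.2.2 | AE |
| Protocol 8.3 | AE, because symptom onset follows the first application |
| Protocol 6.1.1 | Medical history is updated on Day 1 only up to the first dose, so post-dose symptoms fall outside it |
| Protocol 9.4.6 and synopsis | TEAE, by onset or by worsening |
| Protocol 8.1.1 and SAP 12.6.1 | TEAE only if onset follows the first dose; worsening alone does not count |

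Two things follow.

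1. The documents give different answers for this patient and do not rank the rules. Section 6.1.4 is the most specific instruction, so a site may well follow it.
2. A TEAE is a subset of recorded AEs, so no TEAE definition can recover an illness that was entered only as medical history. Correcting 6.1.4 alone is not enough either: under the definition in the SAP, worsening of an infection that began before dosing would be recorded but not tabulated as a TEAE.

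**Scale.** Inputs: about 50 patients randomized 1:1 (Protocol 4.1.2), so about 25 on ATI-1777. Day 1 positivity p is not in the documents; 1% to 5% is an assumption. Expected positives = n × p. Chance of at least one = 1 − (1 − p)^n.

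| p | Expected of 50 | Chance of ≥1 of 50 | Expected of 25 on ATI-1777 | Chance of ≥1 of 25 |
|---|---|---|---|---|
| 1% | 0.5 | 1 − 0.99^50 = 39.5% | 0.25 | 1 − 0.99^25 = 22.2% |
| 2% | 1.0 | 1 − 0.98^50 = 63.6% | 0.5 | 1 − 0.98^25 = 39.7% |
| 5% | 2.5 | 1 − 0.95^50 = 92.3% | 1.25 | 1 − 0.95^25 = 72.3% |

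These figures count positive swabs, not missed AEs. An AE is missed only if the patient also doses before the result, has symptoms after dosing, meets no SAE criterion, and is at a site that follows 6.1.4 rather than the general rules. The table is therefore an upper bound at each p.

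**The case against.** The best defence is that 6.1.4 draws a deliberate line. An infection found on a pre-dose sample was there before treatment; 8.3 itself sends non-serious pre-dose events to medical history, and 6.1.4 cross-refers to 8.3. This holds for the infection. It does not settle symptoms that first appear or worsen after dosing, which 8.3 and 9.4.6 treat as reportable.

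Symptoms could also be entered separately. Section 8.3 prefers a diagnosis to its symptoms only where possible, 8.1.1 counts any unfavorable symptom as an AE, and a complication such as pneumonia is a diagnosis of its own. Section 8.1.4 might also apply, if a positive PCR that leads to discontinuation counts as a laboratory abnormality, which is debatable. These routes exist, but none is stated for this patient and a site could reasonably not use them.

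The case would not be invisible. Reasons for stopping study drug are summarized by arm (SAP 12.1.1), and medical history is summarized and listed (SAP 12.2.2). The AESI category is serious infections, which the SAE route reaches. These points stand and limit the harm, but they do not put the event in the AE tables or the severe-AE count.

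A reader might infer more than the text supports:

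- *That such illness never enters the AE data.* The sections listed above call for it to be recorded; the documents conflict rather than uniformly exclude it.
- *That the infection develops after dosing.* The swab is taken before the first dose, so only symptoms or worsening can follow it.
- *That the sentinel review loses a severe-AE count.* Section 4.1.4 refers to safety data in general; the count is named only in 4.4.2.
- *That there is a 39% to 92% chance of a missed AE.* That is the chance of at least one positive swab in both arms together, under an assumed positivity.
- *That the rule favors one arm.* It applies to both, and randomization balances pre-dose positivity in expectation.

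**Conclusion.** The concern holds as a conflict between sections. Protocol 6.1.4 disagrees with 1.3.2.1, 1.3.2.2, 8.3, 9.4.6 and the synopsis on how to record a non-serious COVID-19 illness whose symptoms start or worsen after the first application in a patient positive on the Day 1 swab. Following 6.1.4 as written can leave that illness, even a severe one, out of the AE and TEAE tables and the four-weekly severe-AE count.

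The number affected is likely small. Under the assumed 1% to 5% positivity, 0.5 to 2.5 of 50 patients are swab-positive, or 0.25 to 1.25 of about 25 on ATI-1777, and only some of them would have an event to miss. Exposure is short because study drug stops once the result is known, and exclusion criteria 14 and 18 already remove known infection and known significant exposure. The point concerns completeness of safety capture and does not affect the primary efficacy analysis.

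**What to change.** Two changes are needed.

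1. In Protocol 6.1.4, replace the recording sentence with a rule to this effect: the positive pre-dose result is kept in medical history; any COVID-19 sign, symptom or worsening with onset on or after the first application is recorded as an AE, with severity, causality and seriousness, whether or not it is serious.
2. Use one TEAE definition throughout. Add the worsening clause of Protocol 9.4.6 and the synopsis to Protocol 8.1.1 and SAP 12.6.1, so that these events are tabulated once recorded.

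The cost is a short protocol edit, an aligned definition in the SAP and a few eCRF entries. The downside is that a few infections acquired before dosing will appear in the TEAE tables and need a footnote. Only recording and tabulation change; the rules for testing, dosing and discontinuation stay as they are.

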6.1.5 Fitzpatrick Skin Type Assessment

Patients' skin type will be classified according to Fitzpatrick skin type at the Screening Visit as follows:

- Type I: Pale white skin, blue/green eyes, blond/red hair. Always sunburns, does not tan.
- Type II: Fair skin, blue eyes. Burns easily, tans poorly.
- Type III: Darker white skin. Tans after initial burn.
- Type IV: Light brown skin. Burns minimally, tans easily.
- Type V: Brown skin. Rarely burns, tans darkly easily.
- Type VI: Dark brown or black skin. Never burns, always tans darkly.

6.1.6 Lesion Photography

Photographs of representative lesions will be taken at each study visit. Sites will be required to submit the patient's baseline photographs to Canfield Scientific's database.

Canfield Scientific will supply all investigational sites with study-specific camera equipment to photograph each patient's identified target AD treatment areas (up to 2 target locations). Sites will be supplied with color stickers to identify each target area. Details regarding the use of the equipment and how to upload the photographs to the Canfield database will be supplied to the sites in the Photography Manual.

6.2 Efficacy Assessments

6.2.1 *Eczema Area and Severity Index*

The EASI (Hanifin et al 2001; Rullo et al 2008) assesses the extent and severity of AD. This study will employ a modified EASI that excludes evaluation of the head (neck, scalp, face), palms of hands, soles of feet, groin, and genitalia. The modified EASI will evaluate AD in each of 3 body regions (trunk [excluding groin and genitalia], upper extremities [excluding palms of hands], and lower extremities [excluding soles of feet]). The EASI scoring system uses a defined process to grade the severity of the signs of AD and the extent affected. If possible, the same individual should conduct the extent and severity evaluations at each visit.

6.2.1.1 *Extent*

Each respective body region will be given a score between 0 and 6 based on the percentage involvement in that region according to [Table 2](#). Precise measurements are not required.

Table 2 Extent of Atopic Dermatitis in Each Body Region

% Involvement	0%	1% to 9%	10-29%	30-49%	50-69%	70-89%	90-100%
Region Score	0	1	2	3	4	5	6

6.2.1.2 *Severity*

For each respective body region, the severity of each of 4 signs (erythema, edema/papulation, excoriation, lichenification) will be graded by the investigator or qualified designee on a 0- to 3-point scale ([0] none, [1] mild, [2] moderate, [3] severe) in AD-affected areas. Half scores are allowed. The average severity across AD-affected areas in each body region will be used as the score for that region.

6.2.1.3 *Score Calculation*

The investigator or qualified designee will enter the extent and severity values into the eCRF. The final EASI score will then be calculated by an electronic data capture system as described in [Table 3](#).

Table 3 EASI Score Calculation

Body Region	Erythema	Edema/ papulation	Excoriation	Lichenification	Area Score	Multiplier	Score
Trunk	(+	+	+)	×	× 0.3	
Upper extremity	(+	+	+)	×	× 0.2	
Lower extremity	(+	+	+)	×	× 0.4	
Final EASI score is the sum of the 3 region scores:							—

EASI = Eczema Area and Severity Index

6.2.2 *Investigator's Global Assessment*

The IGA is the investigator's assessment of the overall appearance of the lesions at a particular point in time. At every study visit, the investigator will assess the IGA using the scale in [Table 4](#) and report the one score that best describes the overall appearance of the lesions. It is not necessary that all characteristics under Morphological Description be present. In indeterminate cases, please use extent to differentiate between scores.

For example:

- Patient with marked erythema (deep or bright red), marked papulation, and/or marked lichenification that is limited in extent, will be considered “3 – Moderate”.

The investigator or qualified designee will enter the score into the eCRF. Whenever possible, the same individual should conduct the evaluation at each visit.

Table 4 IGA Scoring

Score	Morphological Description
0 - Clear	No inflammatory signs of atopic dermatitis (no erythema, no induration/papulation, no lichenification, no oozing/crusting). Post-inflammatory hyperpigmentation and/or hypopigmentation may be present.
1 - Almost clear	Barely perceptible erythema, barely perceptible induration/papulation, and/or minimal lichenification. No oozing or crusting.
2 - Mild	Slight but definite erythema (pink), slight but definite induration/papulation, and/or slight but definite lichenification. No oozing or crusting.
3 - Moderate	Clearly perceptible erythema (dull red), clearly perceptible induration/papulation, and/or clearly perceptible lichenification. Oozing and crusting may be present.
4 - Severe	Marked erythema (deep or bright red), marked induration/papulation, and/or marked lichenification. Disease is widespread in extent. Oozing or crusting may be present.

IGA = Investigator's Global Assessment

6.2.3 *Body Surface Area*

The total percentage of the patient's AD-affected BSA will be estimated by the investigator or designee using the handprint method, which estimates that the area of a patient's full handprint (fingers and thumbs together) constitutes 1% of their total BSA.

The BSA should be calculated for the EASI score using Regional Percentage Estimates as described in the study training video.

Whenever possible, the same evaluator should perform the estimation at each study visit. If new areas of AD develop while the patient is on the study, these new areas will not be assessed.

6.2.4 *Peak Pruritus Numerical Rating Scale*

The PP-NRS ([Yosipovitch et al 2019](#)) is a single patient-reported item designed to measure peak pruritus, or 'worst' itch, over the previous 24 hours based on the following question: 'On a scale of 0 to 10, with 0 being "no itch" and 10 being "worst itch imaginable," how would you rate your itch at the worst moment during the previous 24 hours?'.

Prior to study medication application on Day 1, the study coordinator should show the PP-NRS scale to the patient, explain the scale and ask the patient to indicate which integer best describes the worst pruritus the subject experienced for their AD over the previous 24 hours.

The patient will complete this assessment and record in their diary each morning before applying study medication during the Treatment Period.

The patient will report the diary rating to site staff at each visit, who will enter it into the patient's source documents and eCRF.

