4 STUDY PLAN

4.1 Overall Study Design and Plan

This is a first-in-human, randomized, double-blind, parallel-group, multicenter, vehicle-controlled study to evaluate the efficacy, safety, tolerability, and PK of ATI-1777 solution following twice-daily applications to target areas of male and female patients, aged 18 to 65 years, inclusive, with moderate or severe AD. All AD lesions in protocol allowed areas should be treated. The study will be conducted at approximately 15 sites in the (US).

The study will consist of a Screening Period of up to 30 days, a 4-week Treatment Period, and a 2-week follow-up period. The maximum total duration of the study for patients remaining in the study until their final follow-up assessment will be 73 days.

A study schematic is provided in [Figure 1](#) and a Schedule of Events is provided in [Table 1](#).

4.1.1 *Screening Period*

The investigator will obtain a signed ICF from the patient before any study procedures are performed. For further details regarding the informed consent process, see [Section 10.3](#). Patients will undergo screening evaluations within 30 days of Day 1 to determine study eligibility (see [Section 5](#)). All the results of the screening evaluations should be available at the time that patient eligibility is reconfirmed prior to dosing.

The investigator will maintain a screening log to record details of all participants screened and to confirm eligibility or record reasons for screening failure, as applicable. Certain procedures conducted as part of the participant's routine clinical management and obtained before signing of informed consent may be utilized for screening purposes provided the procedure meets the protocol-defined criteria and has been performed within the timeframe defined in the Schedule of Events ([Table 1](#)).

At the end of the Screening Period, participants meeting all inclusion and no exclusion criteria will enter the Treatment Period.

4.1.2 *Treatment Period*

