Patients will continue treatment of all target areas identified on Day 1, even if the lesion(s) have cleared. If new areas of AD develop while the patient is on study, study medication may be applied to these areas. New areas should be treated at the first sign of disease and continue until the Day 28 visit. New areas of treatment will be recorded in the source notes at the time the patient begins treating them with study medication.

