APPENDIX 2 - PATIENT INSTRUCTIONS

Preparation and General Instructions:

1. Reminder to:
 - a) Refrain from bathing, swimming and/or participating in strenuous exercise that would cause profuse sweating for 6 hours after application of study medication.
 - b) Refrain from applying moisturizers, emollients, and sunscreen to AD treatment areas for the duration of protocol therapy. Moisturizers, emollients, and sunscreens may be applied to non-AD treatment areas.
 - c) Refrain from excessive sun exposure (e.g., sunbathing and/or tanning salon visits) and minimize sun exposure (e.g., wear sun protective clothing, hat) as much as possible.
2. Gather a clean washcloth and towel, the study medication bottle, and dropper.
3. Skin should be clean and dry before applying study medication.
4. Wash your hands with soap and water before and after using this study medication.
5. Record your 'worst' itch over the previous 24 hours on your diary in the morning before applying study medication.
6. Apply a thin layer of study medication to the identified AD target skin area as instructed by the study doctor or the study staff. Keep applying study medication to the area throughout the study, even if the skin begins to clear. If new areas of AD appear, study medication may be applied to these areas.
7. Avoid study medication contact with the eye.
8. You will apply study medication twice a day, approximately 8 to 12 hours apart.
9. Document on your diary whether you completed the morning and/or evening dose and total amount of drug (mL) applied at each application timepoint.
10. Remember to bring your study medication bottles both used and unused to each study visit along with your diary.

Study Medication Application:

1. Draw up exactly 1 mL of study medication into the dropper. The medication level should be at the 1-mL line.
2. During study medication application, avoid any study medication running into your eyes.
3. Squeeze a few drops of study medication onto the center of the identified target AD area and gently rub the study medication into your skin. Keep applying a few drops and rubbing into your skin until **the entire area** is covered with a thin film of study medication.
4. Draw up additional medication 1 mL at a time to cover the entire AD area. No more than a total of 8 mL should be used to treat all affected areas. Less than 8 mL may be used if a lower amount is sufficient to cover all affected skin areas.

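### BSA is defined as total affected area but new AD areas are not scored, so change in BSA omits new disease, and it is unclear whether the rule reaches EASI

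*Protocol*

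**What the plan says.** **Scoring of BSA.** Protocol 6.2.3 starts from a total: "The total percentage of the patient's AD-affected BSA will be estimated by the investigator or designee using the handprint method". It ends with an exclusion: "If new areas of AD develop while the patient is on the study, these new areas will not be assessed". SAP 12.4.4.3 carries both statements unchanged. Change from baseline in BSA at each visit is a secondary endpoint (Protocol 3.2).

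**Treatment of new areas.** Protocol 4.1 says: "All AD lesions in protocol allowed areas should be treated". Section 7.4.1 is permissive in one sentence, "If new areas of AD develop while the patient is on study, study medication may be applied to these areas", and directive in the next, "New areas should be treated at the first sign of disease and continue until the Day 28 visit". It has newly treated areas entered in the source notes. Appendix 2 tells patients: "If new areas of AD appear, study medication may be applied to these areas".

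**Link to EASI.** Protocol 6.2.3 also says: "The BSA should be calculated for the EASI score using Regional Percentage Estimates as described in the study training video". The EASI text itself (Protocol 6.2.1, SAP 12.4.3.2) scores how much of each region is involved and averages severity over the affected skin. It names the body sites left out, and new lesions are not among them.

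**Purpose.** Footnote 8 to the Schedule of Events says these assessments are there to record how severe and how extensive AD is after study medication.

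**The concern.** A total that leaves out part of the affected skin is no longer a total. Baseline BSA counts all AD present on Day 1, while later visits count only what the rater does not regard as new. The endpoint then describes how the Day 1 areas evolved, although its name and definition promise the extent of disease. Spread to a new site, a plain form of worsening, does not register in it.

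Two practical problems follow. First, no text tells a rater how to separate a new area from enlargement of an old one, so the exclusion cannot be applied uniformly. Second, the sentence sits in the section that also refers to the regional estimates for EASI. One rater could carry the exclusion into the EASI area score and another could not. With about 50 patients at about 15 sites (50/15, or roughly 3 per site), randomization stratified only by AD severity, and no site term in the primary model (SAP 12.4.3.4), the plan has nothing that would balance or absorb differing conventions.

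**Working it through.** The plan gives no figure on this point. Its only design figure, 95.6% power for the primary endpoint, is not in dispute. It reproduces with 17 per arm, a difference of 65 - 20 = 45 points, 38.3 used as a standard deviation and one-sided alpha 0.05: noncentrality 45 / (38.3 × √(2/17)) = 3.43 on 32 df, power 95.6%. The power cannot be recomputed for this issue because no new-lesion rate is given.

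**1. BSA within a patient.** Let B be baseline BSA, O the current extent of the Day 1 areas, and N the extent of new areas.

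- Recorded change under the rule = O - B
- Change in total affected BSA = O + N - B
- Gap = N, which is never negative, so the recorded change is never worse than the change in the total.

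Assumed values (not from the documents): B = 10, O = 5.

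| New areas N (% BSA) | Recorded change (points) | Change in total (points) |
|---|---|---|
| 0 | 5 - 10 = -5 | 5 + 0 - 10 = -5 |
| 3 | -5 | 5 + 3 - 10 = -2 |
| 5 | -5 | 5 + 5 - 10 = 0 |
| 8 | -5 | 5 + 8 - 10 = +3 |

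Four different courses receive the same value.

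**2. BSA between arms.** Taking active minus vehicle, the recorded difference equals the difference in total BSA plus (mean N on vehicle - mean N on active). If new areas are equally common the term is zero. If they are commoner on vehicle, the drug's advantage is understated; if commoner on active, it is overstated. The documents give neither mean, so size and sign are both undetermined.

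**3. EASI under the two readings.** Region multipliers are 0.3 (trunk), 0.2 (upper extremity) and 0.4 (lower extremity), from the EASI score calculation tables. Assume each region has area score 1 throughout, a sign sum of 8 at baseline and 4 at Week 4, and that new lesions do not change the averaged severity.

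- Baseline: 8 × 1 × (0.3 + 0.2 + 0.4) = 7.2
- Week 4, new areas left out: 4 × 1 × 0.9 = 3.6, a change of (3.6 - 7.2)/7.2 = -50.0%
- Week 4, a new area takes one region across 10% involvement (area score 1 to 2):
  - upper extremity: 3.6 + 4 × 0.2 = 4.4, change -38.9%
  - trunk: 3.6 + 4 × 0.3 = 4.8, change -33.3%
  - lower extremity: 3.6 + 4 × 0.4 = 5.2, change -27.8%

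In this example the reading alone moves the patient's primary endpoint by 11 to 22 points and decides whether a 50% improvement is reached. It shows what the ambiguity could do in one patient; it does not estimate what will happen in the trial.

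**The case against.** The BSA rule is explicit and identical in both documents. Treating an area without scoring it is not in itself a contradiction. For a locally acting topical drug, following the areas treated since Day 1 is a defensible target, because areas that appear later receive less treatment. EASI has its own section with its own list of exclusions, and on a plain reading it counts all AD in the allowed regions. New disease can also show in IGA, in the source notes, and in discontinuation when worsening requires additional AD therapy (Protocol 5.4.1). Enlargement of Day 1 areas is not excluded from BSA. The eligibility criteria keep out recent flares and unstable AD, and treatment lasts only four weeks, so new areas may be few.

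Much of this stands. The certain effect is on one secondary endpoint, and the training video, which is not among the documents, may already settle the EASI question. The defence of a Day 1-area measure does not stand. Neither document states that target, and it conflicts with the definition of BSA as a total and with the purpose given in footnote 8.

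A reader might go further in three ways that the documents do not support:

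- **That new lesions are likelier on vehicle, so the rule dilutes the treatment difference.** No rate by arm is given. The drug is described as acting locally with minimal or no systemic exposure, so fewer new lesions at untreated sites does not follow.
- **That the primary endpoint excludes new lesions.** The EASI text says no such thing.
- **That the BSA example amounts to a false 50% improvement.** The endpoint is absolute change in BSA, so the recorded value is -5 points.

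**Conclusion.** The point holds for BSA. Followed exactly, the rule yields a change that is not the change in total affected area. The two differ by the full extent of new AD in each patient: 0, 3, 5 or 8 points in the assumed example. This is a stated rule that gives the wrong quantity, and it also lacks any criterion for what counts as new.

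For EASI the finding is an ambiguity only. It arises because the exclusion shares a section with the instruction on regional estimates, and the detail is left to an unseen video. The 11 to 22 point shift depends on the assumed scores and on a rater who applies the exclusion to EASI. The size and direction of any between-arm bias remain unknown on both endpoints. The wording should be corrected, but nothing here shows that the primary comparison is biased.

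**What to change.** Delete the sentence barring assessment of new areas from Protocol 6.2.3 and SAP 12.4.4.3. State there, and in Protocol 6.2.1 and SAP 12.4.3.2, that at each visit BSA and the EASI extent and severity scores cover all AD in protocol-allowed regions, whenever it appeared. Bring the training video into line, and add a clause saying whether IGA is rated on the same basis.

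The cost is an amendment to the wording and a short note to raters. The downside for the sponsor is that change in BSA may look less favourable. A separate BSA for the Day 1 areas could be kept as a supplementary summary, but it means a second estimate at each visit and so some extra assessment work; it is optional.

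This concerns scoring only. The permissive and directive sentences on treating new areas in Protocol 7.4.1 should be reconciled with each other and with Section 4.1 and Appendix 2; no view is taken here on which should prevail.
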